### 2.3.3 Exploratory Endpoints

The exploratory endpoint is the effect of 7 days of treatment with ROSE-010 on body weight, measured as change in body weight from baseline to Day 8.

## 3 STATISTICAL METHODOLOGY

### 3.1 General Considerations

#### 3.1.1 Analysis Day

Analysis day will be calculated from the date of first dose of study drug. The day of the first dose of study drug will be Day 1, and the day immediately before Day 1 will be Day -1. There will be no Day 0.

#### 3.1.2 Analysis Visits

Scheduled visits will be assigned to analysis visits as recorded on the CRF. All scheduled visits will be included within analysis, all unscheduled visits will be listed unless specified otherwise.

### *3.1.3 Definition of Baseline*

Baseline is defined as the last data collection point (assessment) prior to the first dose of ROSE-010 99 mcg, ROSE-010 150 mcg, or placebo.

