#### **7.1.2 Secondary Endpoints**

The secondary endpoints are the following:

- Hunger score on a VAS (0 to 100 mm) measured pre-dose; 20 minutes after study drug administration; and 1.5, 2.5, 3.5, 4.5, 5.5, and 6.5 hours after study drug administration;
- Satiety score on a VAS (0 to 100 mm) measured pre-dose; 20 minutes after study drug administration; and 1.5, 2.5, 3.5, 4.5, 5.5, and 6.5 hours after study drug administration;
- Prospective consumption score on a VAS (0 to 100 mm) measured pre-dose; 20 minutes after study drug administration; and 1.5, 2.5, 3.5, 4.5, 5.5, and 6.5 hours after study drug administration;
- Desire to eat score on a VAS (0 to 100 mm) measured pre-dose; 20 minutes after study drug administration; and 1.5, 2.5, 3.5, 4.5, 5.5, and 6.5 hours after study drug administration;
- Palatability (tastiness) score on a VAS (0 to 100 mm) measured at the start of lunch;
- Incidence and severity of nausea on a VAS (0 to 100 mm) measured pre-dose; 20 minutes after study drug administration; and 1.5, 2.5, 3.5, 4.5, 5.5, and 6.5 hours after study drug administration; and
- Plasma PK analysis of ROSE-010: maximum plasma concentration ( $C_{max}$ ), time to  $C_{max}$  ( $T_{max}$ ), area under the plasma concentration-time curve (AUC), terminal phase elimination half-life ( $t_{1/2}$ ), and other plasma PK parameters.

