#### **7.2.2 Efficacy Visual Analogue Scales**

On Days 1 through 7, the VAS questionnaire to evaluate hunger, satiety, prospective consumption, and desire to eat will be administered pre-dose; 20 ( $\pm 5$ ) minutes after study drug administration;

and 1.5, 2.5, 3.5, 4.5, 5.5, and 6.5 hours ( $\pm 5$  minutes) after study drug administration. On Day -1, the VAS questionnaire to evaluate hunger, satiety, prospective consumption, and desire to eat will be administered 10 ( $\pm 5$ ) minutes prior to the start of lunch and 1, 2, 3, 4, 5, and 6 hours ( $\pm 5$  minutes) after the start of lunch. On Day -1 and on Days 1 through 7, the VAS questionnaire to evaluate palatability will be administered at the start of lunch (see [Appendix A](#)). For details regarding the VAS questionnaire to evaluate nausea, which is a safety assessment, see [Section 8.14](#). VAS questionnaires are provided in [Appendix C](#).

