### **9.2 Statistical Methods**

Study data will be summarized by treatment group using descriptive statistics, figures, and/or raw data listings where appropriate.

Continuous data and change from baseline will be presented in terms of evaluable observations (n), arithmetic mean, standard deviation, median, minimum, and maximum value.

Categorical data will be presented as counts and percentages. When applicable, summary data will be presented by treatment (ROSE-010 99 mcg, ROSE-010 150 mcg, or placebo) and by assessment time. Individual subject data will be listed by treatment, subject number, and, where applicable, by assessment time.

All descriptive summaries and statistical analyses will be performed using SAS version 9.4 or later (SAS Institute, Inc., Cary, North Carolina).

Baseline will be defined as the last data collection point (assessment) prior to the first dose of ROSE-010 99 mcg, ROSE-010 150 mcg, or placebo.

Details of the statistical analyses will be provided in a separate Statistical Analysis Plan.

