### *3.1.4 Summary Statistics*

Data will be presented by treatment (ROSE-010 99 mcg, ROSE-010 150 mcg, or placebo). Categorical data will generally be summarized with counts and percentages of subjects. The denominator used for the percentage calculation will be clearly defined. Continuous data will generally be summarized with descriptive statistics including n (number of non-missing values), mean, median, standard deviation, minimum, and maximum. Change from baseline, defined as the post-baseline assessments subtracted by the respective baseline value, will also be calculated for continuous data and summarized using descriptive statistics.

In the event that a subject takes the wrong study drug (i.e., did not take the randomized study drug), the actual treatment received will be used for analysis.

All descriptive summaries and statistical analyses will be performed using SAS version 9.4 or later (SAS Institute, Inc., Cary, North Carolina).

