##### *3.5.1.2 Secondary Efficacy Analysis*

Observed values and change from baseline values of hunger, satiety, prospective consumption, desire to eat, and palatability (tastiness) scores on a VAS (0 to 100 mm) will be summarized using descriptive statistics for all measured visits and timepoints.

The area under effect (AUE) will also be calculated from time 0 to 6.5 hours (390 minutes) for each VAS scale, except palatability, on Day 1 and Day 7.  $AUE_{0-6.5}$  will be calculated using the trapezoid method. If any observations are missing for the scheduled timepoints for the AUE calculation, the missing values will be imputed using the last observation carried forward (LOCF) method.

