#### 3.6.8 *Other Safety Assessments*

Observed values and change from baseline values nausea scores on a VAS (0 to 100 mm) will be summarized using descriptive statistics for all measured visits and timepoints.

The area under effect (AUE) will also be calculated from time 0 to 6.5 hours (390 minutes) for the nausea scale on Day 1 and Day 7.  $AUE_{0-6.5}$  will be calculated using the trapezoid method. If any observations are missing for the scheduled timepoints for the AUE calculation, the missing values will be imputed using the LOCF method.

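### For hunger, satiety, prospective consumption and desire to eat, change from baseline after lunch is measured against one pre-lunch rating on Day 1, although a meal-matched Day -1 profile is collected

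*SAP*

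**What the plan says.** **Baseline rule.** SAP 3.1.3 states: "Baseline is defined as the last data collection point (assessment) prior to the first dose". Protocol 9.2 carries the same rule ("Baseline will be defined as the last data collection point (assessment) prior to the first dose"), so the SAP does not depart from the protocol here. Neither document has a rule specific to the VAS. SAP 3.1.4 describes change as "defined as the post-baseline assessments subtracted by the respective baseline value" and does not mention matching by time.

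**Rating times.** On Days 1 to 7 each appetite scale is "measured pre-dose; 20 minutes after study drug administration; and 1.5, 2.5, 3.5, 4.5, 5.5, and 6.5 hours after study drug administration" (Protocol 7.1.2). On Day -1, Protocol 7.2.2 schedules the same questionnaire 10 (±5) "minutes prior to the start of lunch and 1, 2, 3, 4, 5, and 6 hours" after lunch begins. Protocol 7.2.1 sets the start of lunch at 30 minutes after the dose.

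**Analysis.** SAP 3.5.1.2 summarises "Observed values and change from baseline values of hunger, satiety, prospective consumption, desire to eat, and palatability (tastiness) scores on a VAS" descriptively, at all measured visits and timepoints. It adds an AUE from 0 to 6.5 hours "for each VAS scale, except palatability, on Day 1 and Day 7". No between-arm estimate is planned for these scales, and no AUE is planned for Day -1.

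**The concern.** Appetite ratings are expected to move with the meal whatever the treatment. A baseline taken before lunch and subtracted from a rating made one to six hours after lunch starts therefore gives a change that contains the meal, the time of day and, in the active arms, the drug. The placebo arm should show a change too, and it is not a treatment response.

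This matters more because the secondary analysis is descriptive by arm, so the within-arm change tables are a main part of what a reader will see. The secondary objectives are worded as assessing efficacy on these scales, yet the SAP plans no difference from placebo for any of them.

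The protocol already collects what would separate meal from drug. SAP section 5 confirms that lunch intake is not measured before the first dose, so the Day -1 ratings are the study's only pre-treatment record of how a subject responds to lunch. Under SAP 3.1.2 and 3.5.1.2 they would at most appear as observed values.

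**Working it through.** The documents give no sample size, effect size or variance for the VAS, so there is no figure to reproduce. Two checks can be made: one from the text alone, one under stated assumptions.

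**1. Alignment with lunch (text only).** Time relative to lunch = time after dose − 30 minutes.

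| Days 1–7, after dose | Relative to lunch | Rated on Day -1? |
|---|---|---|
| Pre-dose | before lunch, no fixed time stated | no |
| 20 min | 20 − 30 = −10 min | yes |
| 1.5 h | 90 − 30 = 60 min | yes |
| 2.5 h | 150 − 30 = 120 min | yes |
| 3.5 h | 210 − 30 = 180 min | yes |
| 4.5 h | 270 − 30 = 240 min | yes |
| 5.5 h | 330 − 30 = 300 min | yes |
| 6.5 h | 390 − 30 = 360 min | yes |

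Seven of the eight daily ratings have a Day -1 partner. The one without a partner, the pre-dose rating, is the one the rule picks on Day 1. The 20-minute rating is also before lunch, so the meal enters the change only from 1.5 hours on.

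Palatability differs. It is rated at the start of lunch, which on Day 1 is after the dose. Its last rating before the first dose is therefore the Day -1 start-of-lunch rating, and the existing rule already matches it.

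**2. What the change contains (assumed values).** Let M be the shift due to the meal and time of day, and d the drug effect in the same direction.

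- Pre-dose baseline: expected change is M + d on active and M on placebo.
- Day -1 matched baseline: d on active and 0 on placebo, if Day -1 has the same meal shift.
- Difference between arms: d in both cases.

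With M = 40 mm and d = 10 mm, for a scale that falls after eating, the pre-dose baseline gives about −50 on active and −40 on placebo; the matched baseline gives about −10 and 0. The meal share of the active-arm change is M/(M + d):

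- 57% (20/35) to 91% (50/55) for M of 20 to 50 mm and d of 5 to 15 mm;
- 40% (10/25) to 67% (10/15) for M = 10 mm;
- 0% if ratings have returned to their pre-meal level (M = 0).

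**3. Precision (assumed correlations, equal variance σ² at both times).** Var(change) = 2σ²(1 − r).

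- Pre-lunch baseline, r = 0.1 to 0.3: 1.8σ² to 1.4σ².
- Matched Day -1 baseline, r = 0.5 to 0.7: 1.0σ² to 0.6σ².
- Smallest reduction: 1 − 1.0/1.4 = 29%. Largest: 1 − 0.6/1.8 = 67%.

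For a difference between 15 active and 10 placebo subjects with an assumed SD of 20 mm, SE = 20 × √(2(1 − r)) × √(1/15 + 1/10):

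| r, pre-lunch | r, matched | SE, pre-lunch | SE, matched |
|---|---|---|---|
| 0.2 | 0.7 | 10.3 | 6.3 |
| 0.3 | 0.6 | 9.7 | 7.3 |
| 0.5 | 0.5 | 8.2 | 8.2 |

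The raw score, with no baseline subtracted, has SE 20 × √(1/15 + 1/10) = 8.2. A change score beats it only when r exceeds 0.5. Using the baseline as a covariate avoids that threshold: the variance is then about (1 − r²)σ², which is 0.75σ² at r = 0.5 and 0.51σ² at r = 0.7.

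**The case against.** The strongest reply is that nothing in the treatment comparison is wrong. The trial is randomised with a concurrent placebo arm, results are shown by arm, and a shift common to the arms cancels in any comparison between them. That stands. A reader might infer that the meal drowns or biases the drug effect. The documents do not support this: it could describe only a within-arm change read without placebo, and they give no VAS magnitudes to show how large the meal shift is. It is plausible soon after lunch and weaker by 5.5 to 6.5 hours.

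A reader might also infer that the Day -1 ratings go unused. That is too strong. They belong to a scheduled visit and fall within the planned observed-value summaries. Observed values and the AUE do not depend on the baseline rule; only the change tables do.

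Day -1 is also an imperfect control. It is the admission day, with no injection. Lunch intake is not weighed that day, although what was eaten affects the ratings that follow. This limits how far a matched change can be read as pure drug effect, but the pre-lunch baseline does nothing to remove the meal either.

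The word respective in SAP 3.1.4 might be read as time-matched. SAP 3.1.3 nevertheless defines a single last assessment, so the point needs settling in the text.

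Finally, the protocol chose descriptive secondary analyses in a study it calls exploratory. AUE on Days 2 to 6 and daily mixed models for the VAS are therefore preferences, not corrections. The argument is also weak for nausea ("Observed values and change from baseline values nausea scores on a VAS" in SAP 3.6.8), because nothing in the documents shows that lunch by itself distorts a pre-meal nausea baseline.

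**Conclusion.** The point holds for hunger, satiety, prospective consumption and desire to eat. The text alone establishes that their baseline is one pre-lunch rating, that a profile matched at seven times is collected on Day -1, and that no change score or AUE uses it as baseline.

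The harm is limited to within-arm change tables from 1.5 hours on that mix meal with drug, and to a probable loss of precision. Randomised differences are unbiased under either baseline, because both baselines precede dosing. Any part of the meal response that the drug alters through intake belongs to the treatment effect.

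The 29% to 67% fall in change-score variance rests on assumed correlations and on equal variances, which is doubtful on a bounded 0 to 100 mm scale. Equal correlations would give no gain. Neither the primary endpoint nor the safety conclusions are touched. This is a cheap improvement to secondary endpoints, not a threat to the trial's validity.

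**What to change.** 1. In SAP 3.1.3 and 3.5.1.2, define baseline for the four appetite scales as the Day -1 rating at the same time relative to lunch. Keep the Day 1 pre-dose rating as baseline only for the pre-dose ratings on Days 2 to 7.
2. Compute AUE from 20 minutes to 6.5 hours on Day -1, Day 1 and Day 7.
3. Report the difference of each dose from placebo in Day 1 and Day 7 AUE with 90% confidence intervals, adjusted for Day -1 AUE and labelled exploratory. This gives 4 scales × 2 days × 2 doses = 16 contrasts. With no true effect, about 16 × 0.1 = 1.6 intervals would be expected to exclude zero by chance, hence the label.
4. Record the change in SAP section 5, because Protocol 9.2 carries the same generic rule.

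Palatability needs no change. Extending the rule to nausea, or the AUE to Days 2 to 6, is optional.

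**Cost.** SAP wording and programming before database lock and unblinding; all the data are already scheduled. **Downsides.** The pre-dose rating has no Day -1 partner, so the matched AUE starts at 20 minutes instead of time 0. The report should also say that Day -1 is an uninjected admission day without weighed lunch intake.

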### *3.1.4 Summary Statistics*

Data will be presented by treatment (ROSE-010 99 mcg, ROSE-010 150 mcg, or placebo). Categorical data will generally be summarized with counts and percentages of subjects. The denominator used for the percentage calculation will be clearly defined. Continuous data will generally be summarized with descriptive statistics including n (number of non-missing values), mean, median, standard deviation, minimum, and maximum. Change from baseline, defined as the post-baseline assessments subtracted by the respective baseline value, will also be calculated for continuous data and summarized using descriptive statistics.

In the event that a subject takes the wrong study drug (i.e., did not take the randomized study drug), the actual treatment received will be used for analysis.

All descriptive summaries and statistical analyses will be performed using SAS version 9.4 or later (SAS Institute, Inc., Cary, North Carolina).

### *3.1.5 Handling of Dropouts and Missing Data*

Date imputations for partial dates and other imputations are described in the respective analysis sections.

## **3.2 Analysis Populations**

### *3.2.1 Per Protocol Analysis Set*

The Per Protocol Analysis Set will include all randomized subjects who have received all doses and have evaluable efficacy data, and no major protocol deviation that significantly affects the evaluability of the subjects in the study.

### *3.2.2 Safety Analysis Set*

The Safety Analysis Set will include all randomized subjects who have received at least 1 dose of study drug (ROSE-010 99 mcg, ROSE-010 150 mcg, or placebo).

Subjects will be analyzed according to the treatment they actually received if this differs from that to which the subject was randomized.

### *3.2.3 Pharmacokinetic (PK) Analysis Set*

The PK Analysis Set will include subjects who have received at least 1 dose of ROSE-010 99 mcg or ROSE-010 150 mcg and have at least 1 measurable post-dose plasma PK concentration.

## **3.3 Subject Data and Study Conduct**

### *3.3.1 Subject Disposition*

Subject disposition will be presented for all randomized/enrolled subjects. The number and percentage of subjects in each of the following categories will be summarized by actual dose group and overall, as appropriate:

- Randomized / enrolled;

- Dosed;
- Completed the study; and
- Prematurely withdrew from the study and the primary reasons for early withdrawal;

### *3.3.2 Protocol Deviations*

Counts and percentages of subjects with CSR-reportable protocol deviations by deviation will be summarized by dose group and in total for the Safety Analysis Set.

All protocol deviations will be listed.

### *3.3.3 Analysis Populations*

Counts and percentages of subjects in each analysis population will be summarized by dose group and in total based on all randomized subjects. Reasons for exclusion from each analysis population will also be summarized.

### *3.3.4 Demographic and Baseline Characteristics*

The following demographic and baseline characteristics will be summarized:

- Age (years)
- Sex
- Race
- Ethnicity
- Height (cm)
- Weight (kg)
- Body mass index (BMI) (kg/m^2)

Demographic and baseline characteristics will be summarized with descriptive statistics or counts and percentages of subjects as appropriate by dose group and in total for the Safety Analysis Set.

### *3.3.5 Medical History*

Medical history will be coded to system organ class and preferred term using the Medical Dictionary for Regulatory Activities (MedDRA) version 27.0. Counts and percentages of subjects with medical history by system organ class and preferred term will be summarized by dose group and in total based on the Safety Analysis Set.

### *3.3.6 Prior and Concomitant Medications*

Concomitant medications will be coded to anatomical therapeutic chemical (ATC) class and preferred term using the WHO Drug Dictionary B3 Global, March 2024G B3.

For summary purposes, medications will be considered prior medications if they stopped prior to the first dose of study drug and concomitant medications if they were taken at any time after the first dose of study drug (i.e., started prior to the first dose of study drug and were ongoing or started after the first dose of study drug).

If a medication has incomplete start or stop dates, dates will be imputed to determine whether a medication should be considered prior or concomitant. If a medication start date is incomplete, the first day of the month will be imputed for missing day and January will be imputed for missing month. If a medication stop date is incomplete, the last day of the month will be imputed for

missing day and December will be imputed for missing month. Incomplete start and stop dates will be listed as collected without imputation.

Counts and percentages of subjects taking prior and concomitant medications by ATC class and preferred term will be summarized by dose group and in total based on the Safety Analysis Set.

#### *3.3.7 Study Drug Exposure and Compliance*

Study drug administration data will be listed by dose group for all subjects in the Safety Analysis Set.

### **3.4 Pharmacokinetic Assessment**

All Pharmacokinetic Assessments will be described in a separate document.

### **3.5 Clinical Efficacy Assessment**

Efficacy analyses will be performed using the Per Protocol Analysis Set.

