### **1.3 Clinical Summary**

The recombinant version of ROSE-010 (LY307161) has been tested in 3 clinical studies. Two Phase 1 clinical studies were conducted to evaluate safety and PK; 1 in healthy subjects, and 1 in T2DM patients. A Phase 2a efficacy study (GL61-001) for the treatment of pain of IBS has been performed in Europe.

LY307161 was generally safe and well tolerated when administered SC in early human clinical studies. Nausea and vomiting were observed as the consistent dose-related side effects of LY307161. Although the majority of subjects tolerated all doses, doses of 500 mcg and greater produced nausea and/or vomiting in the majority of subjects. The maximum tolerated dose was therefore determined to be 400 mcg.

The most frequent adverse events (AEs) in single and multiple dose studies were nausea and vomiting, which occurred at time to peak concentration. These AEs were considered to be dose-related and were of short duration, suggesting a direct pharmacological action of LY307161.

In one study in diabetic patients (H5N-EW-GFFB), a dose-related rise in both supine systolic and supine diastolic blood pressure was observed, which was maximal at 15/11 mm Hg at 450 mcg of LY307161. No rise was demonstrated in standing systolic or standing diastolic blood pressure, and supine blood pressure returned to baseline in approximately 2 hours.

Measurements of antibody titers to LY307161 in diabetic subjects (H5N-EW-GFFB) and IBS patients (GL61-001) prior to exposure to LY307161 and 30 days after the last exposure showed no clinically significant antibody response to LY307161.

Study RP-09-01 was a single-center, randomized, parallel-group, double-blind, placebo-controlled, dose response, PD, and PK study evaluating the effects of ROSE-010 on gastric, intestinal, and colonic transit and gastric volumes in female patients with IBS-constipation (IBS-C). Doses of 30, 100, or 300 mcg ROSE-010 or matching placebo were administered via abdominal SC injection once daily for 3 consecutive days and 1 final day 2 to 10 days later, over a 13-day interval. The results of this study showed that ROSE-010 actually accelerated colonic transit at 48 hours and did not retard colonic transit at the primary colonic transit endpoint at 24 hours. There was no exacerbation of IBS-C bowel symptoms and no significant effect on stool frequency or consistency.

Overall, in the IBS patient populations studied to date there have been no exacerbations of constipation.

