### **4.3 Withdrawal Criteria**

A subject may prematurely discontinue study drug and/or withdraw from the study at any time. A distinction must be made between premature discontinuation of study drug and withdrawal from the study. A subject may prematurely discontinue study drug and still continue his/her participation in the study. Subjects who prematurely discontinue study drug dosing will be encouraged to continue in the study and complete visits and procedures as per Protocol.

The reasons for premature discontinuation of study drug and for withdrawal from the study must be documented in the electronic case report form (eCRF). Reasons include, but are not limited to, the following:

- Withdrawal of consent;
- Any event, laboratory abnormality, intercurrent illness, or other medical condition that indicates to the Investigator that continued participation is not in the best interest of the subject;
- Pregnancy;
- Subject failure to comply with Protocol requirements or study-related procedures;
- Termination of the study by the Sponsor or regulatory authority;
- Initiation of any prohibited medication(s) as described in [Section 5.6.1](#);
- Severe allergic reactions to the study drug; or
- Any stopping rule as described in [Section 3.2](#).

If a subject withdraws prematurely from the study for any reason, study staff should make every effort to complete the full panel of assessments scheduled for Day 8/ET. The reason for subject withdrawal must be documented in the eCRF.

In the case of a subject lost to follow-up, attempts to contact the subject must be made and documented in the subject's records.

Withdrawn subjects may be replaced at the discretion of the Sponsor. Subjects who discontinue for study drug-related safety or tolerability reasons will not be replaced.

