### 5.2 Rationale for Dosing

The rationale for selection of the ROSE-010 dose levels (99 mcg and 150 mcg) is based on the results of Clinical Studies GL61-001, RP-09-01, and RP-23-01 (see [Section 1.3](#) and the ROSE-010 Investigator's Brochure).

The results from Study RP-09-01 showed that 300 mcg and 100 mcg have observable effects on gastric emptying relative to placebo which is known to be directly related to appetite reduction. Nausea and vomiting, known side-effects of GLP-1 treatment, were more frequently reported with the higher dose (300 mcg). The dose selection was confirmed as relevant by the results from the RP-23-01 study. In this study, a trend in dose dependency was noted as well as a decrease overall in food intake relative to placebo with tolerable nausea.

In Study GL61-001 there was no difference in pain relief response 1 hour post-dose between the dose groups 100 and 300 mcg, which were both significantly different from placebo. At 2 hours post-dose, the pain relief response was observed to diverge between the treatment groups with a difference of approximately 10 mm on the visual analogue scale (VAS) (0 to 100 mm). Both groups were significantly superior to placebo at 2 hours post-dose.

In Study RP-23-01, 14 male and female subjects were randomized to receive a sequence of placebo, 100 mcg ROSE-010, and 150 mcg ROSE-010. Eleven subjects completed all 3 treatment periods. There was a signal indicating a possible dose dependency in amount of food consumed, suggesting that ROSE-010 may have a role in weight management and obesity. No safety concerns were raised.

Nausea and vomiting were both more frequently reported with higher dose.

These data show the following:

- There is no difference in pain relief response at 1 hour post-dose between ROSE-010 100 mcg and 300 mcg; and
- The occurrence of the side effects nausea and vomiting is dose dependent with Studies RP-09-01 and GL61-001 showing approximately double the frequency of vomiting in the case of 300 mcg compared with 100 mcg.

In summary, the doses of ROSE-010 99 mcg and 150 mcg are justified as being within a pharmacologically effective range but with a lower risk for side effects as compared to 300 mcg.

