### 2.2 Study Design

#### 2.2.1 Overview

This is a randomized, placebo-controlled, double-blind, parallel-group Phase 2 study evaluating the efficacy, safety, and PK of daily administrations of the GLP-1 analogue ROSE-010 on appetite and food intake in overweight and obese female subjects. The study is planned to include 3 parallel treatment groups, with 40 subjects randomized in a 3:3:2 ratio to receive ROSE-010 99 mcg, ROSE-010 150 mcg, or placebo, respectively, as follows:

- Treatment Group 1: 99 mcg ROSE-010 (15 subjects) administered SC once daily for 7 consecutive days.
- Treatment Group 2: 150 mcg ROSE-010 (15 subjects) administered SC once daily for 7 consecutive days.
- Treatment Group 3: Placebo (10 subjects) administered SC once daily for 7 consecutive days.

For each subject, the study will consist of the following:

- Screening Period (Day -28 to -2) and Check-In (Day -1), during which subjects will be evaluated for eligibility.
- Treatment Period (Day 1 to Day 7), during which subjects will receive 7 once-daily doses of ROSE-010 or placebo, followed by discharge on Day 8.
- Follow-up phone call, which will be completed 7 ( $\pm$ 2) days after the final dose of study drug.

Consenting subjects will be screened for eligibility according to study-specific inclusion/exclusion criteria within 28 days prior to the first administration of study drug (Day 1). Subjects will be admitted to the CPU on Day -1 and will remain confined to the CPU until discharge on Day 8/Early Termination (ET). On Day 1, subjects will be randomized in a 3:3:2 ratio to receive ROSE-010 99 mcg, ROSE-010 150 mcg, or placebo, respectively. Study drug will be administered SC once daily (30 minutes before lunch) for 7 consecutive days (Days 1 to 7). All meals served at the CPU will be standardized and controlled. Subjects will consume as much of the standardized lunch as desired, and food will be weighed prior to and after eating to assess food intake. Assessments of hunger, satiety, prospective consumption, desire to eat, palatability, and nausea will be performed. Blood samples will be collected to evaluate PK. Safety parameters will be monitored.

Subjects will be discharged on Day 8/ET. The end of study follow-up phone call will be completed 7 ( $\pm$ 2) days after the final dose of study drug.

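### Efficacy is analysed only in a Per Protocol set that requires all seven doses, so the primary comparison can depend on who tolerated treatment and no other efficacy population is planned

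*SAP*

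**What the plan says.** SAP 3.5 and Protocol 9.2.1 give the same rule: "Efficacy analyses will be performed using the Per Protocol Analysis Set". SAP 3.2.1 limits that set to "all randomized subjects who have received all doses and have evaluable efficacy data, and no major protocol deviation" affecting evaluability. SAP 2.2.1 fixes what all doses means: "subjects will receive 7 once-daily doses of ROSE-010 or placebo, followed by discharge on Day 8".

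The only other sets are Safety and PK. SAP 3.2.2 reads: "The Safety Analysis Set will include all randomized subjects who have received at least 1 dose of study drug". The Safety set is used for safety only. No full analysis or intention-to-treat set is defined, and no sensitivity analysis of efficacy on another population is planned. SAP 3.1.5 gives no rule for missing food intake.

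Four other places bear on this:

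- Protocol 4.3: "Subjects who prematurely discontinue study drug dosing will be encouraged to continue in the study and complete visits and procedures as per Protocol". The same section says that subjects who stop for drug-related safety or tolerability reasons are not replaced.
- Protocol 1.3: "Nausea and vomiting were observed as the consistent dose-related side effects of LY307161". Protocol 5.2 adds: "The occurrence of the side effects nausea and vomiting is dose dependent".
- SAP 3.5.1.1 analyses lunch intake on Days 1 to 7 with a repeated-measures mixed model at alpha 0.1, reporting p-values and 90% confidence intervals.
- SAP 3.1.4 says that if a subject takes the wrong drug, "the actual treatment received will be used for analysis", without limiting this to safety. Protocol 9.1 states that rule only within the Safety set definition, and SAP section 5 does not list the difference as a change.

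**The concern.** Receiving all seven doses is an outcome observed after randomisation. If nausea leads some subjects to miss or stop doses, and nausea is related to how much they eat, exclusion depends on both treatment and the primary endpoint. What remains is a comparison of subjects who completed dosing, not of the groups as randomised.

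The endpoint is measured at each lunch, which makes the rule stricter than it first looks. A subject who stops after dose 5 has five valid on-drug lunches, and none is used. Even the Day 1 contrast is filtered by what happens on Days 2 to 7. The protocol's effort to keep such subjects under observation adds nothing to the efficacy analysis.

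Randomisation matters more here than usual. SAP section 5 removes baseline food intake from the model because it is not collected before the first dose, so adjustment for baseline intake cannot address imbalance created by selection.

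**Working it through.** **The plan's own figures.** No effect size, SD, power or dropout rate is stated, so only the allocation can be reproduced: 40 × 3/8 = 15, 40 × 3/8 = 15, 40 × 2/8 = 10. It agrees. Everything below is illustration on stated assumptions.

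**1. Data lost per excluded subject.** There are seven lunches. Missing a single dose removes up to 6 lunches that followed a received dose. Stopping after dose k removes k such lunches.

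**2. Precision.** In units of the SD of the analysed outcome, SE = sqrt(1/n_active + 1/n_placebo).

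- 15 vs 10: sqrt(1/15 + 1/10) = 0.408.
- 12 vs 10 (3 lost from one active arm, placebo intact): sqrt(1/12 + 1/10) = 0.428.
- Ratio: 0.428 / 0.408 = 1.05, a 5% rise.

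The difference detectable with 80% power at two-sided alpha 0.10 is (1.645 + 0.842) × SE, which goes from 1.015 to 1.065 SD. Power for a 1 SD difference goes from 78.9% to 75.5% (normal approximation).

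**3. Selection bias.** Assume proneness to nausea is normally distributed with correlation rho to low intake, and that the most nausea-prone fraction d of an active arm is excluded. The mean of those remaining rises by rho × phi(z(1-d)) / (1-d) between-subject SDs:

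| d | rho 0.3 | rho 0.5 | rho 0.7 |
|---|---|---|---|
| 10% | 0.06 | 0.10 | 0.14 |
| 20% | 0.11 | 0.18 | 0.25 |
| 30% | 0.15 | 0.25 | 0.35 |

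**4. Effect on the test.** Simulation of 15 vs 10 subjects with seven lunches each, intraclass correlation 0.6, rho 0.5, exclusion in the active arm only, t-test on subject means, 8,000 runs per scenario. Differences are in single-lunch SDs; negative means less eaten on drug.

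| Excluded | Per Protocol estimate, true 0 | Type I error (nominal 0.10) | Per Protocol estimate, true -0.80 | Power, Per Protocol | Power, all subjects |
|---|---|---|---|---|---|
| 10% | +0.08 | 0.110 | -0.73 | 0.68 | 0.77 |
| 20% | +0.14 | 0.128 | -0.67 | 0.60 | 0.75 |

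Using all subjects, the estimates were +0.01 and about -0.80, with type I error about 0.10. The formula in step 3 agrees: 0.097 × sqrt(0.6) = 0.08 and 0.175 × sqrt(0.6) = 0.14. Two cautions apply. The null shift is towards higher intake on drug, so the added rejections lie on the side unfavourable to the drug. The simulation also lets excluded subjects keep the full drug effect, so it isolates selection and does not model off-drug lunches.

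**5. Timing.** Assume placebo intake 100, tolerators 90, and 2 of 15 who stop, eating 50 while on drug and 100 afterwards. The return to 100 is assumed because Protocol 1.1 gives a half-life of about 1 hour. Per Protocol gives 100 - 90 = 10 throughout. With all subjects included:

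- Day 1: 100 - (13 × 90 + 2 × 50)/15 = 15.3.
- Seven-day mean, stopping after dose 1: their mean is (50 + 6 × 100)/7 = 92.9, so the effect is 100 - (13 × 90 + 2 × 92.9)/15 = 9.6.
- Stopping after dose 2: their mean is 85.7, effect 10.6.
- Stopping after dose 6: their mean is 57.1, effect 14.4.

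The gap is widest on days when those who later stop are still on drug. Over the whole week it can be negligible or change sign.

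**The case against.** The strongest reply is that few subjects may be excluded. They are confined from Day -1 to Day 8, every dose is supervised (Protocol 5.5.4), and treatment lasts seven days. Protocol 5.2 calls nausea tolerable in the earlier food-intake study, and its statement on dose dependence goes on to compare 300 mcg with 100 mcg, whereas this trial uses 99 and 150 mcg. Exclusions are settled before unblinding (SAP 4.2), and their numbers and reasons are tabulated by group (SAP 3.3.3). Per Protocol also addresses a legitimate question, the effect under full dosing, in a study described as exploratory.

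Much of this stands. It limits the likely size and justifies keeping the Per Protocol analysis. It does not remove the problem: a tolerability exclusion is treatment-related even when made blind, and a table of reasons does not show how the estimate moves. The exploratory label does not settle it either, because p-values and confidence intervals are planned for the primary endpoint and the results are meant to support further development (Protocol 1.4).

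Several stronger readings are tempting but unsupported:

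- A reader might infer a 21% loss from the earlier study, where 11 of 14 completed. That was a three-period cross-over, and no reasons for non-completion are given.
- Applying that loss to every arm (about 12/12/8) gives a 12% rise in SE (0.456/0.408), but this needs equal loss on placebo, which drug-related nausea does not imply.
- A reader might conclude from 15.3 vs 10 that a third of the effect disappears. That holds only for days when the subjects who stop are still on drug, and only at those assumed intakes.
- It would be too strong to say that the bias could never be examined. The lunches are collected, so a reanalysis is possible, but it would be post hoc.

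**Conclusion.** The point holds as a defect of the stated rule; its size in this trial is unknown. Whenever treatment-related exclusions occur, the primary comparison is no longer between randomised groups, usable lunches are discarded, and no planned analysis shows the consequence. If everyone receives seven doses and nobody is otherwise excluded, the sets coincide and nothing changes.

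Under assumed exclusion of 10% to 20% of an active arm (rho 0.5, intraclass correlation 0.6), bias matters more than lost numbers: the estimate falls short by about 0.07 to 0.13 SD on a true effect of -0.80. Understatement is not a general result. It follows from assuming that the excluded subjects eat least; if they were weak responders, the effect would be overstated.

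The issue is confined to efficacy: food intake, the appetite and palatability scales, and body weight. Nausea scores and other safety data use the Safety set. The actual-treatment rule in SAP 3.1.4 is a lesser, related matter that applies only if a subject receives the wrong drug.

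**What to change.** Before unblinding, amend SAP 3.2 and 3.5 and Protocol 9.1 and 9.2.1 as follows:

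- Define a Full Analysis Set: all randomised subjects with at least one dose and at least one post-dose lunch measurement, analysed as randomised, using every observed lunch including those after drug discontinuation.
- Make it the primary efficacy set, with the mixed model unchanged.
- Keep Per Protocol as a supportive analysis, described as the effect under full dosing.
- Limit the actual-treatment rule in SAP 3.1.4 to safety and PK, in line with Protocol 9.1.

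The cost is wording and one extra set of tables; no new data are needed. The downside is that the primary estimate may include some off-drug lunches. It then answers a treatment-policy question, and the text should say so, with the Per Protocol result reported alongside. The mixed model's use of incomplete records still rests on missing-at-random, which should be stated too.
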